#### Analysis Sets

- *As Treated (AT) Population*: all patients that were enrolled in the trial for whom the SAPIEN 3 valve implant procedure was begun, defined as the time in which the first Edwards' investigational device is inserted into the patient.

- *Valve Implant (VI) Population:* all AT patient who received and retained the SAPIEN 3 valve upon leaving the procedure room

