#### 7.1.5 Patient Screening and Data Collection

##### 7.1.5.1 Patient Screening and Enrolment

The study site shall have a committed Heart Team involved in the screening process. The Heart Team will include at least two cardiac surgeon, one interventional cardiologist, one radiologist, and one anesthesiologist but could also include (without being limited to) the following specialties:

- Echocardiography
- Gerontology

The screening of patients in cardiovascular and cardiac surgery departments will be conducted by one or more delegated study team members. The study team will be responsible for ensuring and reporting study patient screening for study eligibility. Cumulative screening and enrollment logs will be maintained by study sites. Reasons for screen failures will be documented in study logs.

To accommodate the implant procedure learning curve, a roll-in strategy will be available. Each study site will be allowed up to two roll-in patients. Edwards Lifesciences will document if the patient is a roll-in patient before the implant procedure begins. Roll-in patients will complete all study visits and procedures, and not be counted toward the 60 implanted patients.

In addition, the Heart Team will be required to assess all patients for study inclusion to ensure compliance to surgical risk criteria, screening procedures to assess valve size and delivery method, and other inclusion/exclusion criteria. After heart team identifies a patient, the Sponsor will review and confirm eligibility during the case review process.

All patients who sign a study informed consent will be entered into the database. Subjects will be included

in analysis of the trial if an Edwards' investigational device is inserted into the patient. Only patients that leave the procedure room with a SAPIEN 3 THV in place will be counted toward the 60 implanted patients.

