#### 7.1.5.2 Data Collection

Study subjects will undergo screening and pre-procedure visits, and then follow-up visits at Discharge, and 30 Days (+14 days) for Endpoint analysis. Long-term follow-up data is collected at 6 Months (+/- 30 days), 1 Year (+/- 60 days), 2 Years (+/- 60 days), 3 Years (+/- 60 days), 4 Years (+/- 60 days), and 5 Years (+/- 60 days).

The Study Visit Schedule is outlined in Table 4 for enrolled subjects for the duration of the study from Screening and Baseline through the 30 Day visit (Primary Endpoint) and 5 year follow-up visits.

Table 2. Study Visit Schedule

	Screening	(≤30 days of procedure) Baseline	Procedure	Post-Procedure (Within 48 hours)	Discharge	30 Day Follow-Up (+14 days)	6 Month (+/-30 days)	1 Year (+/-60 days)	2-5 Years (+/-60 days)
Informed Consent	X								
Medical History	X								
Physical Exam	X				X	X		X	X
CSS Angina	X				X	X		X	X
NYHA Classification	X				X	X		X	X
STS Risk Score, Logistic EuroSCORE, and EuroSCORE II	X								
Operability Risk Assessment	X								
Cardiac Medications		X	X	X	X	X	X	X	X
Adverse Event Assessment			X	X	X	X	X	X	X
Frailty Assessment		X							
NIH Stroke Scale		X 		X 	X 	X 			
Modified Rankin Scale		X 		X 	X 	X 			
Six Minute Walk Test (6MWT)		X 				X 			
KCCQ Questionnaire		X				X			
Labs									

Hemoglobin, Hematocrit, Platelet Count and White Blood Cells		X		X	X	X			
PTT or PT/INR		X		X	X				
CK/CK-MB and/or Troponins		X 		X 		X			
Creatinine		X		X	X	X			
Liver Panel (ALT, AST)		X							
Albumin		X				X			
Non-Invasive Tests									
ECG		X		X	X	X		X	
Chest X-ray		X							
Transthoracic Echocardiogram (TTE)	X				X	X		X	X
Fluoroscopic imaging implanted valve			X			X 		X 	X 
Invasive Tests									
CT Thoracic/Abdomen with visualization of iliac and femoral arteries	X								
Cardiac Catheterization or CT angiogram	X								
Supra-aortic Angiogram or (TEE)	X		X						
Invasive hemodynamics			X						

 Collection of adverse events begins when the patient starts the procedure. This is defined as when anesthesia is first administered

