Pre procedure	Aspirin 75-100 mg once daily 
 
• Patients with bare metal stent (BMS) within one month or drug eluting stent (DES) within 12 months should be continued on Clopidogrel/Prasugrel prior to their procedure
 
• Patients in atrial fibrillation on warfarin should be bridged with LMW or UF heparin prior to the procedure
 
• Patients with persistent or paroxysmal atrial fibrillation, not on anticoagulation, will not be required to have a TEE to rule out LA thrombus prior to procedure. If intra-procedural TEE during TAVI reveals thrombus, procedure will be aborted and delayed until patient has been on
 

----------------------	--

	
warfarin or dabigatran for 30 days.
 
 
• In patients under concomitant TAVI/PCI, Clopidogrel loading with either 300mg or 600mg prior to the procedure is recommended in addition to ASA:
 

Intra procedure	Heparin will be given to achieve/ maintain ACT $\geq$ 250 sec.

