### Procedure Assessments

Procedural information, findings, results, and SAPIEN 3 delivery system and device identification will be recorded on the Case Report Form and are listed below:

- Duration of the procedure, defined as the time from skin incision to access closure;
- All cardiac medications and all medications given for cardiovascular effect;
- A supra-aortic angiogram or TEE to assess valve performance and coronary patency
- Fluoroscopic imaging of implanted valve to assess acute deployment (e.g. proper annular placement, fully vs. under deployed, circularity/ovality)
- Contrast media quantity
- Total fluoroscopy time and dose
- Adverse Events

Subjects will be continuously monitored clinically, hemodynamically, and electrocardiographically during the index procedure for all local and systemic side-effects.

It is recommended subjects are monitored in the operating room for at least 15 minutes after completion of the procedure, with special attention to hemodynamic condition and cardiac rhythm. The sheaths may be removed when ACTs reach <150 sec after implantation of the study valve (for non-surgical closures).

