### 8.4 Statistical method for all data, together with deficient, unused or fault data (including drop out and withdrawal) and method for treating unreasonable data

The primary and secondary endpoints will be reported based on the AT Population. Descriptive and summary statistical analysis will be performed on all endpoints. Patient listings for adverse events, deaths, and reinterventions will include all enrolled patients.

All clinically relevant baseline and follow-up variables will be tabulated. Descriptive statistics for continuous variables include mean, standard deviation, sample size, median, minimum, and maximum) and frequency tables or proportions for discrete variables.

Kaplan Meier estimates will be performed at the pre-specified follow-up times to project the estimates for time-related endpoints such as the 30-day mortality rate, the primary endpoint; the standard error and confidence limits will be computed using Greenwood's algorithm. Based on 50 patients as point estimate and length of estimate on the primary endpoint, the 30 days death rate and 95% confidence interval will be summarized.

Echocardiographic data will be analyzed by an Echo core laboratory with respect to the degree of total aortic valve regurgitation (TVR) and paravalvular aortic valve regurgitation (PAR) according to the VARC-2 definitions [29].

These data and other categorical data (e.g., NYHA class) will also be presented as shift from baseline for each of the pre-specified follow-up periods.

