## 10.2 Analysis of the possibility of failure

For the purposes of this study, adverse events that may be anticipated are associated with the use of the SAPIEN 3 THV System as well as the anesthesia and interventional procedures used to deliver and deploy the SAPIEN 3 THV.

Anticipated risks have been minimized to the furthest extent possible, but the nature of the procedure and the severity of the patient's disease state has inherent risks. Exposure to ionizing radiation associated with fluoroscopy, x-rays and CT is no more than is associated with routine clinical practice for transcatheter aortic heart valve replacement.

Risks are outlined in the SAPIEN 3 THV System Instructions for Use (IFU)

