## 13. Provisions on adverse event and device defect report

### 13.1 Adverse events

Adverse events may be volunteered by patients, elicited from questioning by Investigator or delegated study personnel, or collected via observation by the Investigator. In addition, patients will be instructed to contact the investigator, and/or study coordinator if any significant adverse events (e.g., expanded safety composite events) occur between study evaluation visits.

All adverse events are reported from the start of the procedure, which is defined as when anesthesia is first administered, and are reported until subject participation has ended (i.e. completion of the study or withdrawal of consent). Adverse events must be reviewed at every follow-up visit until resolution, AE has stabilized (according to Investigator), or the study has been completed. Should the adverse event be ongoing at time of study completion, the database should be updated to reflect status.

Reporting guidelines for adverse events:

- Record the number of units of blood needed for any transfusion associated with any overt bleeding event

- Failure of a percutaneous closure device shall be reported as an access site vascular closure device complication
- Vascular complications shall be designated as access or non-access related;

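### Patients who die, or whose procedure is abandoned, after first anesthesia but before any Edwards device is inserted are in no endpoint rate and appear only in listings

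*Combined protocol and SAP*

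**What the plan says.** **Entry to the analysis.** Section 8.6 (Analysis Sets) defines AT as enrolled patients "for whom the SAPIEN 3 valve implant procedure was begun, defined as the time in which the first" Edwards investigational device is inserted. Section 7.1.5.1 applies the same rule: a subject counts "in analysis of the trial if an Edwards' investigational device is inserted into the patient". The Valve Implant set is a subset of AT. Roll-in patients are evaluated separately.

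**Use of the set.** Section 8.4 states: "The primary and secondary endpoints will be reported based on the AT Population". The same section extends the listings of adverse events, deaths and reinterventions to all enrolled patients.

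**Start of the procedure.** Section 13.1 states: "All adverse events are reported from the start of the procedure, which is defined as when anesthesia is first administered". Footnote 1 to the visit schedule in 7.1.5.2 agrees: "This is defined as when anesthesia is first administered". A third clock, under Procedure Assessments, serves only to time the procedure: "Duration of the procedure, defined as the time from skin incision to access closure".

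**Risks and aborted attempts.** Section 10.2 attributes anticipated adverse events to the device system "as well as the anesthesia and interventional procedures used to deliver and deploy the SAPIEN 3 THV". The antiplatelet/anticoagulation table in 7.1.5.2 foresees one way an attempt may end early: "If intra-procedural TEE during TAVI reveals thrombus, procedure will be aborted". It then delays the procedure for 30 days of anticoagulant treatment.

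**Follow-up.** The Follow-Up Visits text keeps patients whose study procedure was begun, but who do not retain the valve, until the 30-day assessment or resolution of any adverse event. It does not say which start it means.

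**The concern.** The primary endpoint is all-cause mortality 30 days after the index procedure. The secondary endpoints include mortality at 72 hours, labelled peri-procedural, and absence of procedural mortality within the success composite. By the definition in 13.1, a death after anesthesia has begun is a death during the procedure. If no Edwards device has yet been inserted, that death cannot count in any of these endpoints, because AT entry depends on having reached insertion.

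The trial is single-arm, has 50 to 60 patients and is intended to support approval. In a sample that small, one death visibly moves the headline rate. The word begun also has two meanings in the plan. Under the 8.6 meaning, an abandoned patient has no assured status at day 30, so the missing rate might not be recoverable afterwards.

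**Working it through.** **1. Where each patient goes.** Combining 7.1.5.1, 8.4, 8.6 and 13.1, for a non-roll-in patient given anesthesia:

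| Course after first anesthesia | Adverse events collected | In AT and endpoint rates | In listings |
|---|---|---|---|
| Early complication, device then inserted | yes | yes | yes |
| Dies before any Edwards device is inserted | yes | no | yes |
| Abandoned before any Edwards device is inserted | yes | no | yes |

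The first row follows because AT selects patients and does not set an event window. No text removes an event that precedes insertion once the patient is in AT. The listings apply because 8.6 treats enrolment as separate from, and prior to, insertion.

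**2. How wide the interval is.** The kit in section 5.2 includes the Edwards eSheath and the Edwards balloon catheter. If eSheath insertion counts as the first Edwards investigational device, the gap runs only from anesthesia through imaging and early access. If it does not, the gap extends further into the procedure. The documents do not list which components count.

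**3. The plan's own figures.** The plan gives no figure for this point. The only derivable one in section 8 is drop-out: (60 − 50)/60 = 16.7%, which agrees with the stated bound of under 17%. Sizes of 50 and 60 are used below as illustrative AT denominators.

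**4. Effect of one omitted death.** With *d* deaths among *n* AT patients and *k* omitted deaths, compare *d/n* with *(d+k)/(n+k)*. Section 8.4 plans Kaplan–Meier with Greenwood limits. Without censoring before day 30 the estimate is the simple proportion, and with zero deaths the Greenwood standard error is zero, so exact (Clopper–Pearson) 95% limits are shown instead. For 0/*n* the upper limit is 1 − 0.025^(1/*n*); for *n* = 60 this is 5.96%.

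| AT result | With one omitted death | Change (points) |
|---|---|---|
| 0/60 = 0% (0 to 5.96) | 1/61 = 1.64% (0.04 to 8.80) | 1.64 |
| 2/60 = 3.33% (0.41 to 11.53) | 3/61 = 4.92% (1.03 to 13.71) | 1.59 |
| 0/50 = 0% (0 to 7.11) | 1/51 = 1.96% (0.05 to 10.45) | 1.96 |
| 2/50 = 4.00% (0.49 to 13.71) | 3/51 = 5.88% (1.23 to 16.24) | 1.88 |

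**5. Effect of one omitted survivor.** With two deaths, 2/60 = 3.33% against 2/61 = 3.28%. The omission raises the rate by 0.05 points.

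**6. How likely such a patient is.** The documents give no rate. The chance of at least one is 1 − (1 − *p*)^*n*. For assumed *p* of 0.2%, 0.5% and 1% it is 11.3%, 26.0% and 45.3% among 60, and 9.5%, 22.2% and 39.5% among 50. These are patients of either kind, not deaths.

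**The case against.** The strongest reply is that an exposure-based analysis set and a broad adverse-event clock serve different purposes, and that 7.1.5.1 and 8.6 agree on the analysis rule. That is fair. It is a good reason to keep AT, and it does not give the excluded patients a rate anywhere.

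Four stronger readings may tempt a reader, and the documents do not support them:

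- *All complications before insertion are lost.* They are not. They stay in the AT rates for everyone who later has a device inserted.
- *The omission always flatters the device.* This holds for deaths only. An omitted survivor pushes the mortality rate the other way, though trivially.
- *The cases are concealed.* Consented patients enter the database, adverse events are collected from anesthesia, and the listings cover all enrolled patients.
- *The thrombus provision shows deaths being dropped.* It describes a postponement. The patient may return and enter AT.

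It can also be said that the plan is descriptive, with no hypothesis test, performance goal or success threshold, so no formal decision turns on one case. That stands, and it limits the weight of the point. Day-30 follow-up is likewise covered if begun takes its meaning from 13.1; the difficulty is that the text leaves this open.

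Finally, section 8.5 refers to a more detailed SAP and the contents list an appendix of definitions. Neither is in the text available, and either might settle the matter.

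**Conclusion.** The point holds in a narrow form. Deaths and abandoned procedures between first anesthesia and first Edwards device insertion reach no endpoint rate, because the procedure start in 13.1 precedes the AT entry event in 8.6 and every endpoint is reported on AT.

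The size cannot be derived from the documents, which state neither an expected mortality nor a rate of events before insertion. On assumed counts, each omitted death lowers the reported 30-day mortality by about 1.6 to 2.0 percentage points at 50 to 60 patients, and the confidence intervals overlap heavily. There may be no such patient at all. No stated figure in the plan is wrong. The case for acting is that the loss of deaths from the primary rate is selective and cheap to remove before data are seen.

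**What to change.** 1. Keep AT as defined. Add to 8.6 a safety set of all non-roll-in patients given anesthesia for the index procedure, and report 30-day mortality and the safety endpoints on it beside AT.
2. State in 8.6 which kit components count as the first Edwards investigational device, naming the eSheath explicitly either way.
3. Define time zero for the primary endpoint, including when an attempt is aborted and later repeated. Simply moving the AT start to anesthesia would leave this open: if the clock ran from an attempt aborted for thrombus, the 30-day window could close before the delayed implant takes place. Say also that such a patient is counted once.
4. Reconcile the word begun in the Follow-Up Visits text with 8.6 and 13.1, so that day-30 status is collected for everyone in the safety set.

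The cost is a definition, one extra table column and confirmed day-30 status for what may be very few patients; adverse events are already collected from anesthesia. The reported mortality on the added set may be slightly less favourable than on AT.

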## **9. Data Management**

### **9.1 Data Collection**

Data will be captured and managed through an electronic data capture (EDC) system. Passwords will be issued to appropriate data management personnel to ensure confidentiality and protection of the data by allowing variable levels of access to the computer system.

Electronic CRFs (eCRFs) will be used to collect all patient data during the trial. eCRFs must be fully completed for each patient, and signed electronically by the investigator and/or designee.

The investigator, or an individual designated by him/her, is responsible for recording all data from the trial onto the eCRFs on a dedicated website. The investigator is required to provide an electronic signature on the appropriate eCRF pages to verify that he/she has reviewed the recorded data.

Completed eCRFs will be reviewed at the investigational site and remotely by authorized Edwards Lifesciences personnel at regular intervals throughout the trial. All eCRFs will be tracked at Edwards Lifesciences and missing or unclear data will be requested as necessary throughout the trial.

### **9.2 Missing Data**

All possible steps will be taken to minimize missing data in the study, including monitoring of data forms for completeness and efforts to track and maintain contact with study subjects during the follow-up period.

## **10. Feasibility Analysis**

### **10.1 Successful possibility analysis**

Product handling and procedure guidance are provided in the Training Materials and IFU and will be used for device training to minimize risks associated with device use.

Additionally, efforts will be made to minimize these possible risks through site/investigator selection and management. First, site and investigator selection criteria are established to ensure that the study personnel and their institutions are qualified to screen, perform and manage the study procedures as well as support the associated requirements for research.

Second, the trial management structure is designed to provide disciplined oversight of the trial activities including close monitoring of site and personnel performance and also support opportunities for investigators and study personnel to share best practices through investigator meetings, ongoing education and case reviews.

Site and investigator criteria include the following:

- Interventional cardiologists must be experienced and skilled in percutaneous balloon valvuloplasty.
- Strong interdepartmental collaboration between cardiac surgery and interventional cardiology operators will be assessed by an experienced trial study team. The study site

team must be trained in the use of the investigational devices prior to enrollment of study patients.

- The procedure setting must include a fixed C-arm angiography and PCI imaging capability in the catheterization lab or operative suite and/or a hybrid catheterization/operating room suite.
- The study site must have an operating room.

The study site must have an adequately staffed research department with a minimum of one dedicated study coordinator

## 10.2 Analysis of the possibility of failure

For the purposes of this study, adverse events that may be anticipated are associated with the use of the SAPIEN 3 THV System as well as the anesthesia and interventional procedures used to deliver and deploy the SAPIEN 3 THV.

Anticipated risks have been minimized to the furthest extent possible, but the nature of the procedure and the severity of the patient's disease state has inherent risks. Exposure to ionizing radiation associated with fluoroscopy, x-rays and CT is no more than is associated with routine clinical practice for transcatheter aortic heart valve replacement.

Risks are outlined in the SAPIEN 3 THV System Instructions for Use (IFU)

## 11. Quality control of clinical trials

Clinical sites will be chosen that have proper facilities in place to complete THV procedures. Additional training of appropriate clinical site personnel will be the responsibility of the Sponsor. To ensure proper device usage, uniform data collection, and protocol compliance, the Sponsor will present a formal training session to study site personnel which will review the instructions for use of the device, the Investigational Plan, techniques for the identification of eligible patients, instructions on in-hospital data collection, CT recommendations, echocardiography data collection for core laboratory analysis, methods for soliciting data from alternative sources, schedules for follow-up with the study site coordinators, and regulatory requirements. Detailed feedback regarding completion of forms will be provided by the Sponsor, and through regular site monitoring. Edwards Lifesciences reserves the right to enforce retraining for sites who have demonstrated study or procedure compliance issues.

## 12. Ethical issues and informed consent for clinical trials

### 12.1 Ethical considerations

The SAPIEN 3 THV System is not commercially available in China. The clinical investigation shall be conducted in accordance with the ethical principles that have their origin in the Declaration of Helsinki (as updated in Fortaleza Brazil in 2013) and in compliance with China's Good Clinical Practice (GCP) for Medical Devices and any national regulations.

